IQ lower than 85 (using the Wechsler Intelligence Scale for Children – Fourth Edition (Hong Kong) (WISC-IV(HK))); 4) autism spectrum disorder (previously diagnosed by health care professionals), 5) comorbid acute psychiatric disorder (previously diagnosed by health care professionals); and 6) with a severe physical disability (e.g., blindness, deafness) or learning disability (e.g., dyslexia).

Sample size

The guidelines of Whitehead et al. (2016) suggested that recommended that at least 16 subjects per group for medium effect size in pilot RCT and 15% attrition over time can be expected. A total of 90 participants will be recruited which fulfils the minimum number suggested by Whitehead et al. (2016). 30 participants in the social VR group, 30 in the traditional social skills group and 30 in the waitlist control group. This sample size is comparable to those used in the published pilot study on children with ADHD. For instance, van der Oord et al. (2014) recruited 40 participants (20 in the control group and 20 in the interventional group) to examine the efficacy of computerized executive functioning remediation training with game elements in children with ADHD.

Procedure

Recruitment

Participants will be recruited from six primary schools and community centres. Interested participants or parents who provide written informed consent will be further evaluated for inclusion and exclusion criteria by a trained research assistant. Participants who meet the inclusion criteria in the study will be invited to perform an IQ test at the university at baseline.

Randomisation

Eligible participants will be randomized to the social VR (Social VR) group, traditional social skills training group or waitlist control group. A computer-generator randomiser will be used to generate the random allocation list. The randomisation will be undertaken by another research assistant not directly involved in the study. A number generated by the computer will be assigned to each eligible subject who will be randomly allocated to the three different groups by using the number. The participants and their parents or legal guardians will be blind to the assignment process. Parents or legal guardians will receive an email and a telephone call with notification to Group 1, Group 2 or Group 3.

Social VR Intervention

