The parents or legal guardians of the participants will complete a structured questionnaire at the baseline and after the last session. Demographic information, including age, gender, Medication, ADHD symptoms and game experience will be recorded at the baseline. The questionnaires include questions about social skills and executive functioning. The satisfaction of the participants and their parents or legal guardians towards the training program will be assessed at week 3. The VR sickness of the participant will be evaluated after each session. The assessor will be blind to the treatment condition. The questionnaires will include the following scales:

Primary outcome measure

1. Process evaluation

The process evaluation of the training will be assessed by investigating: (i) training acceptability as measured by the participants' attendance and compliance; (ii) recruitment rate; (iii) participant completion.

(i) Assessment of training acceptability and compliance

The attendance of the participants during the trainings will be recorded. To verify the validity of the findings, training non-adherence of the participants will be terminated which will be stated in the consent form. The absence of any training session will be considered as non-adherence. The participants will be asked about their willingness of partaking in this kind of training by one 7-point Likert scale question which is used to reflect the acceptability to the intervention. The retention rate should be at least 85% according to the feasibility RCT.

The compliance with the training program will be evaluated by the communication log which the parents record their children's daily activity and emotion in the 3-week intervention period. The participants' parents will be reminded to attend the training through telephone in the first four training sessions and WhatsApp or WeChat in the fifth and eighth training sessions. No reminder follow-up will be made in the remaining four sessions. These data will be used to evaluate their compliance.

(ii) Recruitment rate

The recruitment rate is at least 48.5% of all referrals according to the feasibility study.

(iii) Participant completion

Participants attending at least nine (i.e., 75%) of the 12 sessions are considered to have completed the program.

Secondary outcome measure

1. Social Skills Rating Scale (SSRS-P)

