The social skills of the children will be assessed by Chinese-translated SSRS-P which will be scored by the participants' parents before the first session and after the last session. This scale consists of 3 subscales, including self-control, assertiveness and initiative and cooperation, with a total of 31 items. A 3-point Likert scale (never, sometimes, often) is used to score. The SSRS-P is a validated instrument that has been commonly adopted in clinical trials of psychiatric and neurological disorders.

2. Child psychologist's assessment

One child psychiatrist will score the performance of the participants in the 5-minute tasks to obtain an objective evaluation. Broken blinding is unavoidable in child psychiatrist's assessment. To minimise unblinding bias during the assessment, each participant will be identified by a case number.

3. Behaviour Rating Inventory of Executive Function (BRIEF)

Chinese-translated BRIEF used to assess the executive functioning of children which will be scored by the participants' parents before the first session and after the last session. The subscales of inhibitions (16-item) and emotional control (10-item) will be adopted in this study. A 3-point Likert scale (never, sometimes, often) is used to score.

4. Satisfaction

Satisfaction is measured by a 7-point Likert scale, 'What grade would you give to this training program?'. Both participants and parents/ guardians have to answer.

5. Simulator Sickness Questionnaire (SSQ)

The SSQ measures motion sickness or physical discomfort of participants in VR environment. Nine items will be measured, including discomfort, fatigue, headache, eyestrain, sweating, nausea, difficulty concentrating, blurred vision and dizziness, with yes or no questions for each item.

6. Assessment of safety

a) Adverse events

RA1 will ask participants' parents/ guardians, using open-ended questions, whether the participants experienced any adverse events during training. The severity and relationship of the adverse event to the intervention will be documented and investigated.

b) Reasons for withdrawal

When a subject withdraws before completing the study, the reasons for withdrawal will be recorded.

Statistical analysis plan

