All statistical analyses will be performed in SPSS version 26.0 software (IBM Corp, Armonk, NY, USA) and are two-sided with a level of significance of < 0.05 . Demographic information of the participants will be summarised with frequency and percentage for categorical variables. The continuous variables will be summarised by mean and standard deviation. The change between baseline and week 3 within each arm will be tested using t-tests. To examine the between-group difference in terms of measure outcomes from baseline to week 3, repeated analyses of covariance (ANCOVA) with adjustment of baseline characteristics will be conducted. To evaluate the improvement during the intervention period among the three groups, f-tests will be performed on primary and secondary outcome measures at the beginning of the first session and at the end of the last session. An intention-to-treat analysis will be performed. This analysis is regarded as the most appropriate approach to analyse RCT data by the highest-quality journals, which have utilised the CONSORT standard.

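### One missed session triggers termination, yet 9 of 12 sessions counts as completion, so the termination rule would largely determine the primary attendance, completion and retention results

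*Combined protocol and SAP*

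**What the plan says.** The relevant text is in the combined protocol and SAP, mostly under Primary outcome measure, where the primary outcome is a process evaluation made up of attendance and compliance, recruitment rate, and completion.

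- **Termination** (item (i), training acceptability and compliance): "training non-adherence of the participants will be terminated which will be stated in the consent form". The next sentence gives the definition: "The absence of any training session will be considered as non-adherence".
- **Retention target** (item (i)): "The retention rate should be at least 85% according to the feasibility RCT".
- **Reminders** (item (i)): families are reminded for earlier sessions, and then "No reminder follow-up will be made in the remaining four sessions". The resulting data are to be used to judge compliance.
- **Completion** (item (iii)): "Participants attending at least nine (i.e., 75%) of the 12 sessions are considered to have completed the program".

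Three other places matter. Sample size states that "15% attrition over time can be expected". Under Secondary outcome measure, the SSRS-P and BRIEF are "scored by the participants' parents before the first session and after the last session". The Statistical analysis plan compares baseline with week 3 and states: "An intention-to-treat analysis will be performed". It does not say how a terminated child is followed or counted.

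**The concern.** One rule tolerates no absences and the other tolerates three, and both act on the same primary outcome. If training stops at the first absence, the protocol turns one missed visit into permanent non-attendance. A child who misses session 3 and would have attended the other eleven is recorded with two sessions and as a non-completer. The trial could then miss its retention target because of its own rule and not because families find the training unacceptable.

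The reminder taper suffers too. Only children with no absence so far would reach the four unreminded sessions, so compliance without reminders would be measured in a group already selected for perfect attendance.

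There is a further, conditional risk. The time point after the last session is undefined for a terminated child. If such children are not assessed at week 3, outcome data are lost after randomisation in the two trained arms only, because waitlist children have no sessions to miss. That would undermine the intention-to-treat comparison with waitlist, in an unknown direction. Social VR versus traditional training would be affected only if absence differs between those two arms.

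**Working it through.** **Inputs from the documents.** 12 sessions in each trained arm (Methods/ Design); 30 children per arm, so 60 trained and 90 in all (Sample size); completion at nine sessions, termination at the first absence, retention of at least 85% (Primary outcome measure); expected attrition 15% (Sample size).

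**Assumptions.** The documents give no attendance rate. Per-session attendance p is set to 0.90, 0.95 and 0.98. Two models are used: independent sessions, and a beta-binomial with within-child correlation 0.2 to represent absences that cluster in some children.

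**Plan's own figure.** 9/12 = 75%, which reproduces.

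**How the rules interact.** A first absence at session 10, 11 or 12 leaves a child with at least nine sessions, both terminated and a completer. A first absence at session 9 or earlier leaves at most eight, so completion is impossible. Under the rule, completing therefore means attending the first nine sessions without a miss.

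**Formulas, independent sessions.** Never terminated: p^12. Reaches nine under the rule: p^9. Reaches the unreminded sessions: p^8. Reaches nine without the rule: P(Bin(12, p) ≥ 9). Expected number terminated: 60 × (1 − p^12).

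| | p = 0.90 | p = 0.95 | p = 0.98 |
|---|---|---|---|
| Never terminated | 28.2% | 54.0% | 78.5% |
| Nine sessions, with the rule | 38.7% | 63.0% | 83.4% |
| Nine sessions, without the rule | 97.4% | 99.8% | 99.99% |
| Reaches the last four sessions | 43.0% | 66.3% | 85.1% |
| Terminated, of 60 | 43.1 | 27.6 | 12.9 |

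**Formulas, correlation 0.2.** With a = 4p and b = 4(1 − p), where 4 = 1/0.2 − 1, the chance of attending the first k sessions without a miss is B(a + k, b)/B(a, b), B being the beta function.

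| | p = 0.90 | p = 0.95 | p = 0.98 |
|---|---|---|---|
| Never terminated (k = 12) | 54.2% | 74.0% | 88.7% |
| Nine sessions, with the rule (k = 9) | 59.1% | 77.2% | 90.3% |
| Nine sessions, without the rule | 88.5% | 95.0% | 98.2% |

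Non-completion in the second table rises from 11.5%, 5.0% and 1.8% without the rule to 40.9%, 22.8% and 9.7% with it.

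**Attendance needed for 85% retention, if termination counts as loss.**
- Within a trained arm, independent sessions: 0.85^(1/12) = 0.987.
- Pooled over 90 children with no waitlist loss: (0.85 × 90 − 30)/60 = 0.775 of trained children never terminated, so 0.775^(1/12) = 0.979.
- With correlation 0.2, solving for p gives about 0.973 within an arm and 0.958 pooled.

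The same within-arm thresholds apply to the expected 15% attrition: below them, termination alone would exceed it.

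**The case against.** The strongest objection is that the termination sentence is defective. Its grammatical subject is non-adherence, not the child, and no sentence says outright that training stops at the first absence. Recording attendance, tapering reminders and tolerating three absences all fit better with a child who can miss a session and carry on. The consent form, said to carry the rule, was not available to this review and might explain it. This stands as a caution about intent. But a consequence that must be disclosed at consent is most naturally one imposed on the participant. Even on another reading, the clash between one absence and nine of 12 remains, and staff could not apply the text consistently.

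Second, the size is entirely assumed, and clustering softens it. At p = 0.98 with correlation 0.2, 89% are never terminated, above the target, and the loss in completion is about 8 percentage points. That is correct. Even there, non-completion goes from about 2% to 10%, so most of it would come from the rule.

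Third, loss of week-3 data is not stated anywhere; the analysis plan's references to week 3 and to intention-to-treat point the other way. This is fair, and that part of the concern remains conditional.

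Fourth, the willingness item, the parents' communication log, the recruitment rate and the recorded reasons for withdrawal are not driven by the rule. That is true, but none of them restores the sessions a terminated child was not allowed to attend. Nor does intention-to-treat.

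**Conclusion.** The concern holds: the plan is wrong as written. Followed as it reads, it would distort the primary attendance, completion and retention results. Over assumed attendance of 90% to 98%, the rule lowers completion by about 17 to 59 percentage points with independent sessions (99.99 − 83.4 and 97.4 − 38.7), and by about 8 to 29 points with correlation 0.2 (98.2 − 90.3 and 88.5 − 59.1). In every case examined, most non-completion would be produced by the rule. The effect shrinks as attendance nears 99%: with independent sessions at p = 0.99, 88.6% are never terminated.

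These figures rest on three assumptions: that termination means the child's training stops, the attendance rates and correlation chosen, and, for retention only, that termination counts as loss. The inconsistency between the two rules depends on none of them. It must be fixed before enrolment, because sessions withheld by termination cannot be recovered at analysis.

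**What to change.** 1. Delete termination for absence from the protocol and the consent form, and record each absence as outcome data.
2. Keep nine of 12 sessions as the single definition of completion.
3. Collect the SSRS-P, BRIEF and psychiatrist rating at week 3, defined as a fixed date from the start of the intervention period, on every randomised child whatever the attendance.
4. Analyse children in their assigned arm. Use all children randomised to a trained arm as the denominator for its attendance and completion, and all children randomised to each arm for its retention.
5. Report the number of missing week-3 ratings by arm.

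The cost is protocol and consent wording, plus a few extra week-3 assessments for children who missed sessions. The downside is that partial attenders may slightly dilute the estimated effects.

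### One missed session triggers termination while nine of 12 sessions counts as completion, so the primary attendance and completion figures partly reflect the rule and not families' adherence

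*Combined protocol and SAP*

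**What the plan says.** The conflict lies within the primary outcome, under Process evaluation.

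- Part (i), Assessment of training acceptability and compliance, records attendance and says that, to protect the validity of the findings, "training non-adherence of the participants will be terminated which will be stated in the consent form". It then defines the term: "The absence of any training session will be considered as non-adherence".
- Part (iii), Participant completion, says: "Participants attending at least nine (i.e., 75%) of the 12 sessions are considered to have completed the program".
- Part (i) also sets a benchmark: "The retention rate should be at least 85% according to the feasibility RCT". Retention is not defined.
- Reminders are tapered over the course: telephone for the first four sessions, messaging after that, and finally "No reminder follow-up will be made in the remaining four sessions". These data feed the compliance assessment.

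Other text bears on the point. Part (i) has a 7-point willingness question, and the secondary outcomes include 7-point satisfaction ratings from child and parent. Parents keep a "communication log which the parents record their children's daily activity and emotion in the 3-week intervention period". Under Measures, Questionnaires, "The VR sickness of the participant will be evaluated after each session". Under Assessment of safety, b), "When a subject withdraws before completing the study, the reasons for withdrawal will be recorded". The Statistical analysis plan specifies intention to treat.

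The document mentions no make-up sessions or excused absences, and it does not say how a terminated child is counted for attendance, retention or completion.

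**The concern.** The completion rule tolerates three absences and the adherence rule tolerates none. If the adherence rule is enforced, the study itself removes the later sessions in which a child might have shown adherence. Attendance is a stated measure of acceptability and completion is a component of the primary outcome, so both would be partly set by the protocol. A child who would have attended 11 of 12 sessions could be recorded as a non-completer with very few sessions.

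The reminder taper loses value in the same way. Only children with no earlier absence would still be in training when reminders stop, so compliance without reminders would be observed in a selected group. The waitlist arm has no sessions during the three weeks, so the problem is confined to the two training arms.

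**Working it through.** **The plan's own figures.** 3 weeks x 4 sessions = 12 sessions; 9/12 = 75%, as stated; two training arms x 30 = 60 children, and 90 with the waitlist arm.

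**The two rules side by side.** Let a child's first absence fall at session k, with termination at that point. The child has attended k - 1 sessions.

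- k = 1 to 9: at most 8 attended, so completion is impossible.
- k = 10 to 12: 9 to 11 attended, so the child is both terminated and a completer.
- No absence: 12 attended.

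This needs no assumed rate. Attendance of nine to 11 sessions, which part (iii) accepts, can arise only when the first absence falls in the last three sessions.

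**Size for completion and attendance.** Let p be the absence probability per session from any cause. The values of p are assumptions, and sessions are first taken as independent.

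- Terminated at some point: 60 x (1 - (1-p)^12)
- Not completing, literal rule: 60 x (1 - (1-p)^9)
- Not completing, nine of 12 alone: 60 x P(Binomial(12, p) >= 4)
- Mean sessions attended, literal rule: sum of (1-p)^k for k = 1 to 12; without termination: 12(1-p)
- Terminated before the no-reminder sessions (read as sessions 9 to 12): 60 x (1 - (1-p)^8)

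| | p = 1% | p = 2% | p = 5% |
|---|---|---|---|
| Terminated, of 60 | 6.8 | 12.9 | 27.6 |
| Not completing, literal rule | 5.2 | 10.0 | 22.2 |
| Not completing, nine of 12 alone | 0.0003 | 0.004 | 0.13 |
| Mean sessions, literal rule | 11.25 | 10.55 | 8.73 |
| Mean sessions, no termination | 11.88 | 11.76 | 11.40 |
| Terminated before session 9 | 4.6 | 9.0 | 20.2 |

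Absences may cluster within children. With a beta-binomial model and an assumed intraclass correlation of 0.2, non-completion under the literal rule is 3.0, 5.8 and 13.7 of 60, against 0.5, 1.1 and 3.0 under nine of 12 alone. The gap narrows but keeps its direction.

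**Retention, only if terminated children count as not retained and there is no other dropout.** The break-even is the per-session absence at which expected retention equals 85%.

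- Training arms only, independent sessions: 1 - 0.85^(1/12) = 1.35%.
- All 90 children with the 30 waitlist children retained: the training arms need (0.85 x 90 - 30)/60 = 0.775, so 1 - 0.775^(1/12) = 2.1%.
- With intraclass correlation 0.1 or 0.2: 2.0% or 2.7% for the training arms; 3.2% or 4.2% for all 90.

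The range is therefore about 1.35% to 4.2%.

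**The case against.** The strongest reply is that the termination sentence is garbled. Its grammatical subject is non-adherence, and it does not say whether training, follow-up or use of the data ends. It defers to a consent form that was not available, so an exception there cannot be ruled out. The nine-of-12 rule and the reminder taper both fit better with children continuing after an absence, so a drafting slip is plausible. This lowers confidence that a one-absence rule would be enforced. It does not remove the conflict: even with termination set aside, one absence is non-adherence while three absences still allow completion.

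The willingness and satisfaction ratings are separate evidence on acceptability, so attendance does not carry that judgement alone. They do not repair the attendance and completion figures, and the plan does not say whether terminated children would answer them. Intention to treat keeps terminated children in the effect analysis but cannot restore sessions they were barred from. The sponsor's validity aim is legitimate, but stopping children preserves the full dose only among those who remain.

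A reader might infer two stronger points that the documents do not support.

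- **The 85% retention benchmark is in jeopardy.** Retention is undefined. A child stopped from training could still be assessed at week 3 and count as retained, and no absence rate is given.
- **VR sickness will drive terminations in the VR arm.** No text says symptoms will cause absences and no frequency is given. Sessions are capped at 20 minutes partly to avoid physical effects, and sickness is checked after each one.

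**Conclusion.** The inconsistency is real and rests on the text alone. Followed as written, the rule makes completion impossible after a first absence in sessions 1 to 9 and sets later attendance to zero, so two primary measures in the training arms partly reflect the rule. The size depends on an absence rate that the plan does not give. Over assumed rates of 1% to 5% per session, the literal rule leaves 5.2 to 22.2 of 60 children not completing if sessions are independent, or 3.0 to 13.7 with intraclass correlation 0.2. Nine of 12 alone leaves at most 3.0 in these scenarios.

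The effect on retention is conditional on how terminated children are counted, and its break-even range does not show that the benchmark would be missed. Nor is it established that the sponsor would wrongly judge the program unacceptable, given the separate ratings. The point should be corrected before the trial relies on these figures. Confidence is medium because of the wording of the termination sentence and the unseen consent form.

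**What to change.** In part (i), delete termination for a missed session. State that the child continues training and is assessed at week 3, and make nine of 12 the single threshold for adherence and completion. Align the matching sentence in the consent form. To serve the sponsor's validity aim, report the number of sessions attended alongside the intention-to-treat analysis.

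The cost is a few sentences of wording, with no new visit or measure; attendance is already recorded. The downside is that some children will receive fewer than 12 sessions, which part (iii) and the intention-to-treat analysis already allow.

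Optional additions are a reason code for each absence on the attendance record and separate reporting of absences related to VR symptoms.

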Social VR intervention is developed to enhance the social interaction skills of children. The participants will wear a head-mounted display (HMD) for the Social VR intervention. Each session of the Social VR intervention lasts for a maximum of 20 minutes to ensure the participants focus on the intervention and prevent causing any physical effect. The duration will be adjusted depending on the emotion of the participants during the intervention. The Social VR intervention will mainly help the participant to enhance their social interaction skills and executive function. The intervention contains three real-life virtual scenarios, including (1) classroom and playground, (2) MTR station and compartment, and (3) street and building. One scenario will be adopted in each session. The sequences of the scenarios used in each session will be the same for all participants. During the Social VR intervention, one RA will also appear as one avatar in the scenario to guide the participants to complete a series of tasks. Each intervention session will be conducted in a classroom independently for each participant.

Traditional social skills training

An experienced SEN teacher will teach the participants social interaction skills through tradidactic instructions and role-play activities. Four modules will be covered in the 3-week training: (1) how to introduce yourself and basic social skills; (2) how to listen to others; (3) how to share with others; (4) learn to know how people feel and how to empathise. These modules have been applied in many studies. The content of this training will be as similar as possible to the Social VR training. The training lasts 20 minutes which depends on the emotion of the participants. Each training session will be conducted in a classroom independently for each participant.

Waitlist control group

The participants in this group will receive no training and they can participate in the social VR training after the intervention period. To ensure consistency of the experiment, the participants are not allowed to initiate or change their pharmacological treatment during the 3-week intervention period.

Measures

Questionnaires

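### Compliance, part of the primary process evaluation, is assigned to a parent log with no stated training content, and no provision is made for recording what each session delivered

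*Combined protocol and SAP*

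**What the plan says.** Under Primary outcome measure, the first process-evaluation item is "training acceptability as measured by the participants' attendance and compliance". The subsection on assessing acceptability and compliance then names several sources.

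- **Attendance:** "The attendance of the participants during the trainings will be recorded". Missing any session counts as non-adherence.
- **Willingness:** one 7-point Likert question, used for acceptability.
- **Compliance:** "The compliance with the training program will be evaluated by the communication log which the parents record". The stated content is "their children's daily activity and emotion in the 3-week intervention period". No training item, scoring rule or threshold is given.
- **Reminders:** a schedule of telephone and messaging prompts to parents, stopping before the last four sessions, followed by "These data will be used to evaluate their compliance".

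Completion is defined separately as attending nine or more of the 12 sessions.

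The intervention sections describe what the child is meant to comply with. In the VR arm a research assistant (RA) guides the child as an avatar, sessions are capped at 20 minutes, and "The duration will be adjusted depending on the emotion of the participants during the intervention". In the traditional arm a special-needs teacher leads, and "The training lasts 20 minutes which depends on the emotion of the participants". Of the setting, the plan says "Each training session will be conducted in a classroom independently for each participant"; the VR section says the same of its own sessions. No home practice is described. Neither arm's section provides for recording minutes or content delivered.

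**The concern.** The instrument and the thing to be measured do not match. Compliance with training happens in a classroom session run by staff. The instrument named for it is kept by a parent, who is not described as being present, and its stated subject is the child's day and mood. Followed as written, it is not designed to show whether the child took part in the training or how much of it was given.

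Attendance does not close the gap, because an attended session has no fixed length or content. Two children with identical attendance may have had quite different amounts of training, and the data as planned could not tell them apart.

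Two things are at stake. First, a component of the primary process evaluation would rest on data not described as measuring it, in a trial whose main purpose on the primary outcome is to learn how the training can be delivered and taken up. Second, when the VR and traditional arms are compared on social skills, there would be no record of training time with which to interpret a difference or its absence.

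**Working it through.** **Inputs**

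- Sessions: 3 weeks × 4 per week (Methods/ Design).
- Session length: at most 20 minutes in VR, and 20 minutes subject to emotion in traditional training (the two intervention sections). No minimum is given for either arm.
- Completion: 9 of 12 sessions (Participant completion).
- Mean delivered length: not given. I assume 5, 10, 15 or 20 minutes to show the range.

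**Step 1. The plan's own figures.** 3 × 4 = 12 sessions, and 9 / 12 = 0.75. The stated 75% reproduces. It counts sessions, not minutes.

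**Step 2. Reference exposure.** 12 × 20 = 240 minutes. This is a ceiling in the VR arm and the nominal total in the traditional arm.

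**Step 3. Minutes delivered = sessions attended × mean minutes per session.**

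| Mean minutes (assumed) | 9 sessions | % of 240 | 12 sessions | % of 240 |
|---|---|---|---|---|
| 5 | 45 | 19% | 60 | 25% |
| 10 | 90 | 38% | 120 | 50% |
| 15 | 135 | 56% | 180 | 75% |
| 20 | 180 | 75% | 240 | 100% |

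Every cell in the table counts as completion. A child with full attendance at 15 minutes and a child with nine sessions at 20 minutes both receive 180 minutes, though their attendance is 100% and 75%. The table applies equally to either training arm.

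**Step 4. What each planned source can show.**

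| Source | Shows | Does not show |
|---|---|---|
| Attendance | whether the child came | length or content of the session |
| Willingness question | attitude to the training | what was delivered |
| Reminder data, if used | staff contact with parents; with attendance, whether the child came as prompts were withdrawn | what happened in the session |
| Parent log, as described | daily activity and emotion | no stated training content |

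No row covers delivery within the session. If the rule ending participation for non-adherence is applied to any absence, attendance will also vary little among the children who remain, so most of the variation in exposure would lie inside sessions. How that rule fits with the 9-of-12 completion definition is a separate matter that the sponsor needs to reconcile.

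**The case against.** The strongest reply is that compliance is not left to the log alone. Attendance is recorded within the same outcome, and the sentence "These data will be used to evaluate their compliance" follows the reminder schedule, so it may refer to reminders, the log, or both. One fair reading is that compliance includes whether families keep attending as prompts are withdrawn. The completion rule is also based on sessions by choice. This stands in part: the log is not the only source. It does not remove the point, because none of the other sources records what was delivered within a session.

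A reader might infer three stronger things that the documents do not support.

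- **That the log holds nothing about the training.** The form is not shown. A record of daily activity could mention sessions, and emotion is the factor said to govern their length. What can be said is that no training content is stated.
- **That VR children would receive less training.** The wording differs between arms (a cap in one, a nominal length in the other), but length depends on emotion in both. No figure in the documents supports a difference, and shortening only the VR arm in a calculation would merely restate that assumption.
- **That unequal minutes would invalidate the VR-versus-traditional comparison.** The Statistical analysis plan specifies intention-to-treat, which validly compares the two programmes as delivered, including their flexible length. Delivered minutes bear on why a difference arose. The social-skills measures are also secondary outcomes here.

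The objection also bears on the remedy. Defining compliance as minutes divided by 240 would score a session shortened as the protocol permits as the child's failure. A proportion of tasks completed would not be comparable across arms, since a series of tasks is described only for VR.

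**Conclusion.** The concern holds as a measurement problem of moderate weight that should be corrected. Compliance is assigned to an instrument with no stated training content. Attendance and any reminder data do not show delivery within a session, and no provision is made for recording it although session length may vary in both training arms.

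The possible size is a child with 100% attendance, counted as having completed, who receives 120 to 180 of 240 minutes (50% to 75%). This rests on assumed mean sessions of 10 to 15 minutes in whichever arm; the documents give no actual durations, so it illustrates what could go unseen and does not predict it. The conclusion does not depend on these values, only on length being variable and its recording not being provided for. Sample size and error rates are unaffected.

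**What to change.** Add a short session record, completed for every session by the person delivering it (RA for VR, teacher for traditional training), with:

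1. start and stop time;
2. whether the planned scenario (VR) or module content (traditional) was completed;
3. the reason for any shortening.

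In the primary outcome section, base the compliance evaluation on attendance plus this record, and state in advance how it will be summarised. Keep the parent log as descriptive context. State which data the sentence after the reminder schedule refers to.

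Report delivered minutes by arm as exposure, separately from compliance, so that a permitted shortening is not scored as non-compliance. Use them to help interpret the intention-to-treat comparison, which stays as it is. The session-length rules and the completion definition need not change for this.

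The cost is a brief entry per session by staff who already run it, plus a wording change. The downside is minor extra data entry. The record should be in place before training starts, since session length and content cannot be reconstructed reliably afterwards.
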